2.0 STUDY OBJECTIVES

1. To estimate the capacity of metformin to mitigate radioactive iodine therapy-induced myelosuppression as assessed by CBC
2. To assess the capacity of metformin to mitigate known side effects of radioactive iodine therapy including xerostomia, xerophthalmia, and dysgeusia as assessed by standardized questionnaire
3. To analyze changes in serum and salivary exosome profiles following a trial of metformin administration in patients receiving radioactive iodine treatment

2.1 Primary Objective:

We have chosen complete blood count (CBC) as our primary endpoint and serum and salivary exosome profiles as secondary endpoints. To evaluate if treatment with metformin inhibits RAI-induced myelosuppression and induces faster recovery of white blood cell count to baseline values, the blood counts will be compared in the pre- and post-treatment samples. Blood parameters will include hemoglobin, red blood-cell count, white blood-cell count, absolute neutrophil count, absolute lymphocyte count, and

Thomas
Jefferson
University

platelet count. Blood and salivary samples will be drawn before surgery, before and immediately after treatment with metformin and RAI, and every three months thereafter for one year.

All blood samples will be taken by a phlebotomist or trained personnel. A baseline blood sample, consisting of two tubes of 1 cc of whole blood each, will be drawn before thyroidectomy as part of standard procedure at patients' pre-operative testing appointment. Patients will recover for a period of 6-8 weeks and identical samples will be drawn within 72 hours of starting metformin. Then samples will be drawn within three days before and within three days after RAI treatment, at the conclusion of metformin treatment, and every three months thereafter for one year. Blood parameters will include hemoglobin, red blood-cell count (RBC), white blood-cell count (WBC), absolute neutrophil count (ANC), absolute lymphocyte count (ALC), and platelet count. Assays will also be conducted on samples to assess metformin-induced changes in serum and salivary cytokines and growth factors, erythrocyte sedimentation rate (ESR), exosome evaluation, and metabolomics profile. 5 cc samples of patient saliva will be collected in specimen cups.

2.2 Secondary Objective:

- Assess safety and tolerability of metformin treatment in subjects undergoing RAI treatment for differentiated thyroid cancer
- To estimate the effect of metformin treatment on symptoms of xerostomia, xerophthalmia and dysgeusia as assessed by the Xerostomia Questionnaire (XQ), the modified Vanderbilt Head and Neck Cancer Symposium Survey (version 2.0), University of Washington Quality of Life Questionnaire, and EORTCQLQ-H&N35

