Diagnosis and Main Inclusion Criteria	Subjects with a biopsy proven diagnosis of differentiated thyroid cancer, and who have a scheduled appointment for definitive resection of the tumor followed by treatment with radioactive iodine at TJUH are eligible to participate.
Study Therapy, Dose, Route, Regimen	Metformin is the therapeutic agent in the protocol. The initial starting dose will be 500 mg orally daily for 3 days which then will be increased to 500 mg twice daily and, if tolerated, further increased to 1000mg twice daily after day 6. Subjects will maintain 1000 mg twice a day dosing or highest tolerated dosing until two weeks post radiation. Subjects will be randomized to 1:1 to take metformin or placebo.
Duration of administration and follow-up	The initial starting dose will be 500 mg orally daily for 3 days which then will be increased to 500 mg twice daily and, if tolerated, further increased to 1000 mg twice daily after day 6. Subjects will maintain 1000 mg twice a day dosing until two weeks post radioactive iodine treatment. The participant's medical records will be reviewed every three months, surveys administered, and CBC repeated over the course of one year according to the schedule outlined below
Reference therapy	None

Statistical Methodology	
The primary objective of the study is to estimate the impact of metformin on complete blood count and serum exosome profile following radioactive iodine treatment. All patients from whom samples are obtained both pre- and post-treatment will be included in the primary analyses. Blood counts will be compared between the RAI/Metformin group (N=16) and the placebo control RAI group (N=16). The estimated mean difference and associated 95% confidence interval will be calculated.
 
Analysis of secondary outcomes will be primarily descriptive and related to taste disturbance, xerostomia, and xerophthalmia.

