1.1 Specific Aims and Hypothesis

Primary:

- To estimate the impact of metformin on radiation-induced myelosuppression in patients treated with RAI after surgery for differentiated thyroid cancer.
- To estimate the effects of metformin on serum and salivary exosome profile in patients with well-differentiated thyroid cancer treated with total thyroidectomy and radioactive iodine.

Secondary:

- To assess safety and tolerability of metformin treatment in subjects with thyroid cancer.
- To assess the effect of metformin therapy on RAI-induced xerostomia, xerophthalmia, and dygeusia as measured by Xerostomia Questoinnaire (XC), the modified Vanderbilt Head and Neck Cancer Symposium Survey (version 2.0), University of Washington Quality of Life Questionnaire, and EORTCQLQ-H&N35

Correlatives:

- To assess the results of the radioactive iodine treatment in patients treated with metformin compared those not treated based on the outcomes of the radioactive iodine scan.

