3.2 Primary Study Endpoints

- complete blood count
- serum and salivary exosome profile

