7.2 Statistical Methods

The primary objective of the study is to estimate the impact of metformin on change in complete blood count. Longitudinal measures of CBC will be modeled using mixed effects linear regression. Outcomes will be transformed as necessary (e.g., log transformed) prior to analysis. Fixed effects will include time (Pre-resection, Post-resection, 3 months post-resection, 6 months post-resection, 12 months post-resection), treatment (metformin vs. control) and treatment by time interaction. We will use a linear contrast to test the null hypothesis that change from pre-resection to post-resection is the same in the control and metformin groups. Secondary analyses will compare groups with respect to change from pre-resection to each of the follow-up times. Components of complete blood count will be analyzed with similar models.

Other longitudinally measured continuous outcomes will be modeled using mixed effects linear regression and longitudinally measured binomial and ordinal outcomes will be modeled using generalized linear mixed effects regression.

7.3 Subject Population(s) for Analysis:

All randomized participants with any data will be included in the analysis as randomized. Missing outcome data will not be imputed.

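### The primary endpoint is inconsistent and cannot be analysed as written: exosome profiles change status between sections, and CBC is six counts with no lead count named

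*Combined protocol and SAP*

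**What the plan says.** **Exosome profiles.** Their status depends on the section read.

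| Place in the combined protocol and SAP | Status of exosome profiles |
|---|---|
| Study Summary, Statistical Methodology | Primary, serum only: "estimate the impact of metformin on complete blood count and serum exosome profile following radioactive iodine treatment" |
| 1.1 Specific Aims, under Primary | Primary, serum and saliva: "To estimate the effects of metformin on serum and salivary exosome profile in patients with well-differentiated thyroid cancer" |
| 3.2 Primary Study Endpoints | Primary, serum and saliva: "serum and salivary exosome profile" |
| 2.1 Primary Objective | Secondary: "We have chosen complete blood count (CBC) as our primary endpoint and serum and salivary exosome profiles as secondary endpoints" |
| 2.2 and 3.3 (secondary objective and endpoints) | Not listed |
| 7.2 Statistical Methods | Not named: "The primary objective of the study is to estimate the impact of metformin on change in complete blood count" |

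**Blood counts.** Section 2.1 defines the content of CBC: "Blood parameters will include hemoglobin, red blood-cell count (RBC), white blood-cell count (WBC), absolute neutrophil count (ANC), absolute lymphocyte count (ALC), and platelet count". Section 7.2 then gives one primary comparison: "We will use a linear contrast to test the null hypothesis that change from pre-resection to post-resection is the same" in the two groups. It adds: "Components of complete blood count will be analyzed with similar models". No count is designated as the lead, no composite is defined, and no alpha level, testing order or adjustment is given.

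**Sample size.** Section 7.1 takes a standardized effect of at least 0.78 SD from the cited retrospective study, without naming the count, and sizes the trial so that a 95% interval has that half-width.

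**The concern.** Two gaps meet in the primary analysis. First, a reader cannot tell whether there is one primary domain (blood counts) or two (blood counts and exosomes), nor whether saliva belongs to the second. Second, section 7.2 treats CBC as a variable distinct from its components, but no such variable exists. A linear contrast needs a single numeric outcome, so someone must pick a count, and the plan does not say which.

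If that choice is made after results are available, the headline estimate may be the most favourable of six. An interval selected in that way no longer has its nominal 95% coverage, and the effect estimate it carries into a later trial is likely to be too large. Section 5.9 adds to the exposure: patients are blinded, but the principal investigator and the care providers making assessments are not.

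**Working it through.** **1. The plan's own figure.** Inputs from 7.1: half-width 0.78 SD, 95% interval, 10% attrition, two equal groups. In SD units of the change score, half-width = t(0.975, 2n − 2) × √(2/n).

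- n = 13 per group: 0.810
- n = 14 per group: 0.777

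So 14 is the smallest n that meets 0.78. Allowing for attrition, 14 / 0.90 = 15.6, rounded up to 16 per group and 32 in total. The plan's numbers reproduce. They apply to one outcome analysed once.

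**2. Can the primary contrast be run as written?** Section 7.2 needs one outcome. Section 2.1 supplies six, unranked. Section 7.1 does not identify the count behind 0.78 SD, so the sample-size section does not settle the matter either.

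**3. Size of the problem if any count could be claimed.** Three assumptions, none stated in the documents: each count is tested two-sided at 5% (inferred from the 95% intervals and the absence of any adjustment), there is no true effect on any count, and one significant count would be presented as the primary result.

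Independent counts: 1 − 0.95^6 = 0.265.

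Correlated counts: simulation of six two-sample t tests, 14 per group, 40,000 runs, with assumed correlations because the documents give none.

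| Assumed correlation between counts | Chance of at least one false positive |
|---|---|
| 0 | 26.5% |
| 0.3, all pairs | 24.6% |
| 0.5, all pairs | 21.2% |
| 0.7, all pairs | 17.0% |
| 0.9, all pairs | 11.2% |
| Mixed pattern* | 21.7% |

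*Hemoglobin–RBC 0.85, WBC–ANC 0.9, WBC–ALC 0.5, ANC–ALC 0.15, platelets 0.2 with each, other pairs 0.1.

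**4. What each remedy costs in precision.**

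- One named count: half-width 0.777 SD at 14 per group; sample size unchanged.
- Six co-primary counts with Bonferroni, 0.05 / 6 = 0.0083: half-width 1.079 SD at 14 per group. Holding 0.78 SD would need 25 per group; 25 / 0.90 = 27.8, so 28 per group and 56 in total.

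**5. Which sample is the primary time point?** The times in 7.2 are pre-resection, post-resection, and 3, 6 and 12 months post-resection. Between surgery and the first three-monthly visit, 2.1 schedules four draws: before metformin, before radioactive iodine (RAI), after RAI, and at the end of metformin. Section 7.2 does not say which of these is *post-resection*. Two of the four precede RAI. Naming a count without naming a sample would leave the primary comparison open.

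**The case against.** The strongest reply is that this is a pilot, framed mainly as estimation and sized for interval width rather than power, so familywise error control is not obligatory. That carries weight, and it is why the percentages above describe exposure rather than a violated standard. It does not remove the point: 7.2 commits to a hypothesis test, the protocol calls itself a pilot efficacy trial, and even pure estimation needs a named outcome.

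A second reply is that blood counts are plainly the lead domain. Sections 2.1 and 7.2 say so, section 5.3 describes the primary endpoint as marrow suppression, and 7.2 fixes one contrast and calls the later times secondary. This narrows the freedom to choose. It does not reconcile the Summary, 1.1 and 3.2, and it does not pick among six counts.

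Three stronger readings are tempting, and the documents do not support them.

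- A reader might infer that the plan states a 5% error rate and breaks it. No alpha appears anywhere, and 7.2 does not call each component a primary test.
- A reader might infer that exosomes have no analysis at all. Section 7.2 has a general provision for other longitudinal continuous outcomes that could cover them; what is missing is any named exosome variable.
- A reader might take 26% as the expected error. It requires independence, which is implausible because WBC includes ANC and ALC.

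The choice of WBC is also open to argument. Section 2.1 singles it out only for recovery to baseline, and section 1.2.2 reports that the most prominent decrease in the cited study was in ANC.

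**Conclusion.** The point holds as a defect of endpoint definition. Exosome profiles are primary in three places and secondary in one, and the statistical section specifies no variable for them. The primary contrast is placed on a panel of six counts, so it cannot be executed without an unplanned choice.

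Under the assumptions in step 3 of the working, the chance of at least one false positive is about 11% to 26% for correlations from 0.9 to 0. It would approach 5% only as the counts became perfectly correlated. The sample-size arithmetic is correct and is not in dispute. The matter should be settled before outcomes are compared by arm.

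**What to change.** - In the Summary, 1.1, 2.1, 3.2, 7.1 and 7.2, name one count as the single primary outcome. WBC is the best supported: 2.1 refers to its recovery, and the between-group results reported from the cited retrospective study are for it. The sponsor should confirm that it is the count behind the 0.78 SD, or justify another.
- In 7.2, tie the *post-resection* time to one scheduled post-RAI sample.
- Report the other five counts as secondary, with 95% intervals and no efficacy claim.
- Make exosome profiles secondary or exploratory throughout, state whether saliva is included, and add them to 2.2 and 3.3, where they are now absent.

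The cost is wording only. Recruitment stays at 32. The sponsor gives up the option of claiming success on a different count.

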3.0 STUDY DESIGN

3.1 General Design

Type of trial: Pilot Efficacy trial

Planned accrual period: 48 months

Planned follow-up period: 12 months

Planned enrollment: Total of 32 patients

Schema of the trial design, procedures, and stages:

Patients with a diagnosis of well-differentiated thyroid cancer who have undergone tumor resection and have indications for RAI treatment that meet our inclusion and exclusion criteria will be offered participation in this clinical trial. Patients who present to TJUH with a known diagnosis of differentiated thyroid cancer who plan to undergo surgical resection followed by radioactive iodine will be offered enrollment in the trial at the time of surgical scheduling. Patients who undergo lobectomy for atypia of undetermined significance/follicular lesion of undetermined significance or follicular neoplasm/suspicious for follicular neoplasm who are subsequently found to a malignancy will be offered enrollment at their first follow-up visit. After informed consent is signed and study subjects are randomized 1:1 to take metformin or placebo, patients will be administered metformin with dose escalation as tolerated until time of RAI treatment. There is no dose escalation for patients randomized to the placebo arm. Pre-operative and pre-RAI treatment CBC with differential will be compared to post-RAI treatment lab values. Standardized surveys assessing symptoms of xerostomia, sialadenitis, xerophthalmia and dysgeusia will be completed.

Participants' Follow-up: Participants' will have blood and saliva samples drawn post-op before metformin administration, before and immediately following RAI treatment, after metformin, and then every three months for 12 months. They will complete surveys at each post-op visit, and their medical records will be reviewed every 3 months for 12 months to assess for symptoms of myelosuppression, xerostomia, xerophthalmia, and dysgeusia. This will allow us to assess the radioprotective effects of metformin post-RAI treatment.

Purpose of the study: To estimate the radioprotective effect of metformin in subjects with differentiated thyroid cancer by evaluating both the ability of metformin to mitigate known side effects of radioactive iodine therapy as well as alter the exosome profile in the serum.

3.2 Primary Study Endpoints

- complete blood count
- serum and salivary exosome profile

3.3 Secondary Study Endpoints

- Measures of
 - a) xerostomia
 - b) xerophthalmia
 - c) dysgeusia

Correlative

- To assess the results of the radioactive iodine treatment in patients treated with metformin compared those not treated based on the outcomes of the radioactive iodine scan.

3.4 Primary Safety Endpoints

Toxicity will be evaluated using the most recent version (version 3) of the NCI toxicity criteria, i.e. the NCI Common Terminology Criteria for Adverse Events (CTCAE) version 4.0. The CTCAE provides descriptive terminology and a grading scale for each adverse event listed. A copy of the CTCAE can be found at <http://ctep.cancer.gov>. Any grade 3 or 4 SAE will require immediate notification to the DSMB and IRB. Metformin will be held for any grade 3 or 4 SAE.

4.0 SUBJECT SELECTION AND WITHDRAWAL

4.1 Inclusion Criteria

1. Diagnosis: Subjects with a diagnosis of differentiated thyroid cancer who have undergone total or near-total thyroidectomy and are candidates for I-131 treatment at TJUH are eligible to participate.
2. Age: Subjects must be ≥ 18 years of age and ≤ 90 years old.
3. Disease Status: Subjects must be diagnosed with differentiated thyroid cancer
4. Prior Therapy: Patients must have previously undergone or plan to undergo thyroidectomy. For those patients who have previously undergone surgery, pre-operative labs, including complete blood cell count with differential must be available.
5. Patients who have a negative urine pregnancy test prior to enrollment. This should be done as part of pre-admission testing prior to surgery (within 14 days of study enrollment).
6. Informed Consent: All subjects must be able to comprehend and sign a written informed consent document.

4.2 Exclusion Criteria

1. Subjects who are pregnant or may become pregnant during metformin administration in accordance with radioactive iodine treatment guidelines.
2. Subjects on metformin for any reason during the preceding 4 weeks.
3. Diabetic subjects are eligible if they are not taking metformin, insulin or sulfonylureas.
4. Subjects who have received iodinated contrast dye. Metformin treatment can be started the day after subjects complete iodinated contrast treatment. If a CT scan with contrast is scheduled after screening and consent, the metformin treatment should be stopped the day before iodinated contrast administration. Metformin can be resumed on the day after last iodinated contrast was administered to the subject.
5. Patients with history of hepatic dysfunction or hepatic disease and abnormal liver function tests (previously documented alanine aminotransferase greater than 40 IU/dL and/or plasma aspartate aminotransferase greater than 45 IU/d). Patients who have a history of hepatic dysfunction or hepatic disease but whose most recent liver function tests have been documented as normal will be eligible to participate.
6. Patients with plasma creatinine level greater than 1.3 mg/dL.
7. Patients with plasma alkaline phosphatase greater than 190 IU/dL.
8. Patients with plasma bicarbonate less than 22 mEq/L or history of lactic or any other metabolic acidosis.
9. Patients with history of congestive heart failure.
10. Patients with myocardial ischemia or peripheral muscle ischemia.
11. Patients with sepsis or severe infection.
12. Patients with history of lung disease currently requiring any pharmacologic or supplemental oxygen treatment.
13. Patients with a current history (in the past 30 days) of heavy drinking which is defined in accordance with CDC definition as more than 8 drinks per week for women and more than 15 drinks per week for men. A standard drink contains .6 ounces of pure alcohol. Generally, this amount of pure alcohol is found in 12-ounces of beer, 8-ounces of malt liquor, 5-ounces of wine, 1.5-ounces or a "shot" of 80-proof distilled spirits or liquor (e.g., gin, rum, vodka, or whiskey). While on study, patients should limit their alcohol consumption to no more than 8 drinks per week for women and no more than 15 drinks per week for men. Patients who feel they cannot comply with this recommendation are not eligible.
14. Patients with a systemic disease that could affect their bone marrow or peripheral blood cells (e.g. systemic lupus erythematosus, human immunodeficiency virus infection, rheumatoid arthritis)
15. Patients who have received or will receive medication that could affect their hematologic state (tyrosine kinase inhibitors, cytotoxic chemotherapy)
16. Patients who are Non-English speaking

*Note: This is due to the nature of the study and the process for full translations of the study documents.

All medications other than those that may cause myelosuppression are permitted except those that are contraindicated with metformin under current FDA recommendations. It is important to note that the medications that are contraindicated with metformin are contraindicated due to concern for theoretical interactions. The following is a list of medications identified as class C (monitor therapy) and class D (consider therapy modification) when treatment with metformin is considered (Patients taking class D medications who are unwilling/unable to switch to alternative therapy will be excluded):

Class C	Class D
ACE Inhibitors, Alpha-lipoic acid, Androgens, BuPROPrion, Carbonic Anhydrase Inhibitors, Cephalexin, Dalfampridine, Dofetilide, Glycopyrrolate (Systemic), Hyperglycemia-Associated Agents, Hypoglycemia-Associated Agents, LamoTRIgine, MAO Inhibitors, Ondansetron, Pegvisomant, Quinolone Antibiotics, Salicylates, Selective Serotonin Reuptake Inhibitors, Thiazide and Thiazide-Like Diuretics, Topiramate, Trimethoprim, Trospium, Vandetanib, Verapamil	Cimetidine, Dolutegravir, Iodinated Contrast Agents, Ranolazine

4.3 Gender/Minority/Pediatric Inclusion for Research

This protocol will include women, minorities and pediatric cases (participants between 18 and 21 years). The incidence of thyroid cancer among women in the United States is 20.3 per 100,000 compared to 6.8 per 100,000 among men making it almost three times as common among women. (Ryerson 2016) Thus, when enrolling patients, by the nature of this disease the study will include significantly more women than men. Differentiated thyroid cancer occurs less frequently in pediatric than in adult subjects. All women and pediatric patients between 18 and 21 who meet the inclusion criteria will be approached for inclusion in the trial.

Inclusion of women plan: we will actively monitor the enrollment of women in the study continuously throughout the enrollment phase. We will ensure that women are actively

recruited and that their enrollment in the study during that time frame reflects the 3:1 incidence ratio of the disease.

